## 8 Definitions

### 8.1 Study day

Study day 1 is the date of first administration of study drug.

The study day for an event that occurs prior to study day 1 will be calculated as (date of event – date of first administration of study drug).

The study day for an event that occurs on or after study day 1 will be calculated as (date of event – date of first administration of study drug) + 1.

### 8.2 Baseline

For efficacy and safety evaluations, the last available pre-dose assessment within 20 days prior to study Day 1 is taken as “baseline” assessment. For MRI and ECG, the last available pre-dose evaluation prior to study Day 1 will be taken as “baseline” assessment. If several measurements are taken on the same day, the last one prior dose is used as measurement of that day.

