3.1 Study design

This is a proof of concept, open-label, single arm, sequential dose-escalation, multi-center study to assess the safety/tolerability and efficacy of 10-weeks treatment of LCI699 followed by a 12-week treatment period in patients with Cushing's disease.

The study will consist of a screening period of up to 60 days (to allow an adequate washout period for any medications that modify cortisol levels), a 10-14-day baseline period, a 10-week sequential dose escalation treatment period, a 12-week treatment period on the last efficacious dose, an End of Treatment-Core evaluation and two optional extensions. Patients are to have an end of study (EOS) visit 28 days after the last drug administration.

With [Amendment 4](#), approximately 15 new patients (not previously enrolled) with Cushing disease will be enrolled as the expansion cohort. Patients who previously completed the trial prior to [Amendment 4](#) and benefited from the treatment with LCI699 will also be allowed to re-enter the study as the core PoC follow-up cohort. These patients will start the study over again at screening and follow through the visit schedule the same as new patients with certain differences described below. Core PoC follow-up patients can reenter if their UFC is > ULN and all other eligibility criteria have been met.

Screening and baseline period:

Patients who meet the eligibility criteria at screening and are either not on medications that effect cortisol levels or have completed the required washout period of these medications, will proceed to baseline evaluations. Patients will be instructed in the proper method for collecting 24 hour urine and saliva. Every 7 days during the baseline period, patients will collect a morning and evening saliva sample (upon waking and just prior to bedtime e.g. 6-8:00 and 23-24:00, respectively). In addition, the patient will perform at least three 24 hour urine collections. Patients will bring in their urine collection bottles on Day -7. At this time, baseline safety and PD samples will be collected. All baseline evaluation results must be reviewed, and confirmation of inclusion/exclusion criteria determined prior to the patient starting dosing with LCI699. Patients will receive medication for the next 2 weeks on Day 1.

Dose escalation period:

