3.2 Rationale of study design

The design of this study addresses the primary objective of reduction of UFC in patients with Cushing's disease, and takes into account the rarity of this disease and the objective nature of the measurement. A dose titration design was chosen for this proof-of-concept study because it provides a fast yet reasonable first approximation of dose-response, and allows individualization of therapy for this disease. Cushing's disease patients are scarce and compared to a parallel dose-response study, this design uses fewer patients, yet allows the testing of multiple doses. In addition, as the level of cortisol can be extremely varied in patients with Cushing's disease due to tumor size and degree of compensatory mechanisms, dose titration to efficacy will reduce unwanted side effects and also reflects clinical practice for the treatment of this disease. While such a design inherently shows that higher doses are the most effective, especially if the pharmacodynamic response is time-dependent, this design can provide valuable data to aide dose selection for a subsequent parallel dose-response study. Given the objective nature of the UFC measurement, an open-label, non-comparator design was chosen to further reduce patient numbers in this proof of concept study. Twenty-four hour UFC measurements were chosen for the primary outcome measure of the study as it is a well-accepted measure of disease activity and allows for the circadian variability and pulsatile

nature of ACTH secretion in patients with Cushing's disease. The mean of 3 UFC measurements will be used to account for the intra-patient variability in the 24-hour UFC measurement in patients with Cushing's disease.

[Amendment 4](#) introduces an additional 12 week treatment period following the 10 week dose-escalation phase. The aim of [Amendment 4](#) is to confirm the preliminary observations from the proof of concept evaluation and evaluate the long term efficacy and safety of LCI699 in patients with Cushing's disease. In particular, this extended treatment with LCI699 will help address questions on the sustainability of cortisol reductions (or escape) and the effect of LCI699 therapy on steroid hormones of the HPA-axis and metabolic effects. Two consecutive, optional long-term extensions (extension-1 and extension-2) will further establish the safety and efficacy profile of LCI699 in patients with Cushing disease.

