4.1 Inclusion criteria

Patients eligible for inclusion in this study have to fulfill **all** of the following criteria at the screening or baseline visit as described in the [Assessment Schedules](#):

1. Written informed consent must be obtained before any assessment is performed.
2. Male or female patients aged 18 - 75 years
3. Patients must have **confirmed** Cushing's Disease that is persistent or recurrent as evidenced by:
 - UFC >1.5XULN (Mean value of three 24-hour urine samples collected within 14 days) [For Patients who completed the first 10 weeks of treatment prior to [Amendment 4](#) (Core PoC follow-up cohort), the appropriate washout of medical treatment for Cushing's disease has to be followed per inclusion criteria 5. These patients must have UFC >1 X ULN (Mean value of three 24-hour urine samples collected within 14 days).]
 - Morning plasma ACTH above lower limit of normal
 - Confirmation of pituitary origin of excess ACTH by at least one of the following three:
 1. History of MRI confirmation of pituitary adenoma (greater than or equal to 6 mm) with positive dynamic test (e.g. CRH or high dose dexamethasone suppression test)or
 2. History of inferior petrosal sinus sampling in patients with a tumor less than 6 mm that meet any of the following criteria with either CRH or DDAVP (desmopressin) stimulation:
 - Central to peripheral ACTH ratio ≥ 2 at pre-stimulation baseline, or
 - Central to peripheral ACTH ratio ≥ 3 after CRH stimulation.or
 3. Prior pituitary surgery with histopathology confirming an ACTH staining adenoma
 - Patients are permitted to washout current drug therapy to meet these entry criteria if they have a known diagnosis of Cushing's disease
4. Patients with de novo Cushing's disease can be included only if they are not considered candidate for surgery (e.g. poor surgical candidates, surgically unapproachable tumors, patients who refuse to have surgical treatment or surgical treatment is not available)
5. For patients on medical treatment for Cushing's disease the following washout periods must be completed before baseline efficacy assessments are performed
 - Inhibitors of steroidogenesis (ketoconazole, metyrapone): 1 week
 - Dopamine agonists (bromocriptine, cabergoline), PPAR-gamma agonists (rosiglitazone, pioglitazone): 4 weeks
 - Octreotide LAR, Pasireotide LAR and Lanreotide autogel: 8 weeks
 - Mifepristone, Lanreotide SR: 4 weeks
 - Octreotide and Pasireotide (immediate release formulation): 1 week

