Treatment	Day 70	Pre-dose ¹	x	106	x	114	x	121
Treatment	Day 98	Pre-dose ¹	x	150	x	161	x	172
Treatment	Day 126	Pre-dose ¹	x	151	x	162	x	173
Treatment	Day 154	Pre-dose ¹	x	152	x	163	x	174
Extension-	Day 182	Pre-dose ¹	x	153	x	164	x	175
Extension-1	Day 210	Pre-dose ¹	x	154	x	165	x	176
Extension-1	Day 238	Pre-dose ¹	x	155	x	166	x	177
Extension-1	Day 266	Pre-dose ¹	x	156	x	167	x	178
Extension-1	Day 294	Pre-dose ¹	x	157	x	168	x	179
Extension-1	Day 322	Pre-dose ¹	x	158	x	169	x	180
Extension-1	Day 406	Pre-dose ¹	x	159	x	170	x	181

Study Phase			Urine Aldosterone (5ml)	Sample Number	Urine Sodium/Potassium (20ml)	Sample Number	Urine deoxycorticosterone (5ml)	Sample Number
Treatment	Day	Time						
Baseline	Day -14 to 0	n/a	x	101	x	108	x	116
Extension-1	Day 490	n/a	x	160	x	171	x	182
Extension-2 ^x	Every 3 months	Pre-dose ¹		2186-2191	x	2192-2197	x	2198-2203
Extension-2 ^x	Every 6 months	Pre-dose ¹		2204,2205,2206...	x	2207,2208,2209...	x	2210,2211,2212...
Ext-2 EoT	EOT	Pre-dose ¹		1201	x	1202	x	1203
EOS	EOS	n/a		107	x	115	x	122

1= urine sample collected for the 24 hours prior to am dose of clinic visit

X= to be collected every 3 months for the first 18 months and every 6 months until EOT for extension-2

Saliva Log: Time schedule for saliva sampling pharmacodynamic (PD)

Study Phase		Saliva Sample			
Treatment	Day	Time	Sample No	Time	Sample No
Baseline	-14	06-08:00	601	23-24:00	602
Baseline	-7	06-08:00	615	23-24:00	616
Baseline	-1	06-08:00	627	23-24:00	628
Treatment	6	06-08:00	639	23-24:00	640
Treatment	13	06-08:00	653	23-24:00	654
Treatment	20	06-08:00	667	23-24:00	668
Treatment	27	06-08:00	681	23-24:00	682
Treatment	34	06-08:00	695	23-24:00	696
Treatment	41	06-08:00	709	23-24:00	710
Treatment	48	06-08:00	723	23-24:00	724
Treatment	55	06-08:00	737	23-24:00	738
Treatment	62	06-08:00	751	23-24:00	752
Treatment	69	06-08:00	765	23-24:00	766
Treatment	76	06-08:00	779	23-24:00	780
Treatment	83	06-08:00	793	23-24:00	794
Treatment	90	06-08:00	797	23-24:00	798
Treatment	97	06-08:00	799	23-24:00	800
Treatment	104	06-08:00	801	23-24:00	802
Treatment	111	06-08:00	803	23-24:00	804
Treatment	118	06-08:00	805	23-24:00	806
Treatment	125	06-08:00	807	23-24:00	808
Treatment	132	06-08:00	809	23-24:00	810
Treatment	139	06-08:00	811	23-24:00	812
Treatment	146	06-08:00	813	23-24:00	814
Treatment	153	06-08:00	815	23-24:00	816
Ext-1	181	06-08:00	817	23-24:00	818
Ext-1	209	06-08:00	819	23-24:00	820
Ext-1	237	06-08:00	821	23-24:00	822
Ext-1	265	06-08:00	823	23-24:00	824

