### 7.3.2.2 Treatment effect on steroid hormones of HPA-axis

Descriptive statistics will be generated for the change from the respective baselines to different time points in mUFC, plasma adrenocorticotrophic hormone (ACTH), serum cortisol, and steroid hormones, plasma 11-deoxycortisol, 11-deoxycorticosterone, salivary cortisol and aldosterone (morning and evening), urine creatinine, plasma and urine sodium, plasma and urine potassium, plasma renin, testosterone, estradiol, insulin, LH, FSH, IGF-1, free T4, TSH, two-sided 95% CIs using exact method will be provided for the changes from baseline.

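### SAP 8.2 uses only the last baseline saliva sample although the protocol schedules two to three baseline saliva days, a modest and avoidable loss of precision in salivary cortisol and aldosterone changes

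*SAP*

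**What the plan says.** - **Baseline rule (SAP 8.2).** "For efficacy and safety evaluations, the last available pre-dose assessment within 20 days prior to study Day 1 is taken as" baseline. MRI and ECG differ only in having no 20-day limit. For repeats within a day: "If several measurements are taken on the same day, the last one prior dose is used as measurement of that day".
- **Saliva collection (Protocol 3.1).** "Every 7 days during the baseline period, patients will collect a morning and evening saliva sample". The baseline period lasts 10 to 14 days. The saliva log in Protocol Appendix 1 lists "Baseline -14 06-08:00 601 23-24:00 602", then "Baseline -7 06-08:00 615 23-24:00 616", then Day -1 at the same two clock times. SAP Table 8-1 places Visit 2 on Days -14 to -1.
- **Use of saliva (SAP 7.3.2.2).** Change from baseline, with 95% confidence intervals, is reported for "salivary cortisol and aldosterone (morning and evening"). SAP 3.2 keeps this secondary objective in the Final CSR. SAP 8.7 bases intervals for change on the t-distribution.
- **Where the SAP averages.** UFC (SAP 8.4) and blood pressure (SAP 7.5.3). There is no such rule for saliva.
- **Washout (Protocol 4.1, criterion 5).** For patients on medical treatment, "washout periods must be completed before baseline efficacy assessments are performed".

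**The concern.** The protocol explains why it averages urine collections: "The mean of 3 UFC measurements will be used to account for the intra-patient variability in the 24-hour UFC measurement". A single saliva sample at one clock time also varies within a patient, and the repeats needed to reduce that noise are already scheduled. SAP 8.2 nevertheless takes one of them.

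In the extensions, each later value is also one sample per clock time. A change is therefore one single sample minus another. The same baseline value is subtracted at every later visit, so its error moves a patient's whole series of changes up or down together, and more follow-up visits do not remove it. Precision is scarce: the Amendment 9 rationale gives 19 patients enrolled under Amendment 4, with 10 still ongoing on 03 May 2018.

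A second gap lies in the same section. Read literally, the same-day rule makes the 23-24:00 sample the value for Day -1, whereas SAP 7.3.2.2 reports morning and evening separately. SAP 8.2 does not say that baseline is set by clock time.

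**Working it through.** The documents state no variance, power or precision figure for saliva, so there is no plan figure to reproduce. The question is how much the choice of baseline changes the interval width.

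**Inputs from the documents**
- Baseline days available, k: 3 under the Appendix 1 log. A 10-day baseline with sampling every 7 days may give 2.
- Baseline days used by SAP 8.2: 1.
- Follow-up samples per visit and clock time in the extensions: 1.

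**Assumptions**
- Within-patient variance of one sample is set to 1.
- τ is the between-patient variance of the true change on that scale, taken as 0, 1 or 2.
- ρ is the correlation between errors on the baseline days, taken as 0, 0.3 or 0.5.
- The mean level is stable over the baseline period.

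**Formula.** Var(change) = 1 + [1 + (k − 1)ρ]/k + τ. With one baseline day this is 2 + τ. With three independent days it is 4/3 + τ. A simulation of 400,000 draws at τ = 0 gave 2.00 and 1.33. The interval-width ratio is the square root of the variance ratio.

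| Days averaged | ρ | τ | Variance ratio | Interval narrower by |
|---|---|---|---|---|
| 3 | 0 | 0 | 1.333/2 = 0.667 | 18% |
| 3 | 0 | 1 | 2.333/3 = 0.778 | 12% |
| 3 | 0 | 2 | 3.333/4 = 0.833 | 9% |
| 3 | 0.3 | 0 | 1.533/2 = 0.767 | 12% |
| 3 | 0.5 | 0 | 1.667/2 = 0.833 | 9% |
| 3 | 0.5 | 1 | 2.667/3 = 0.889 | 6% |
| 3 | 0.5 | 2 | 3.667/4 = 0.917 | 4% |
| 2 | 0 | 0 | 1.5/2 = 0.750 | 13% |
| 2 | 0 | 2 | 3.5/4 = 0.875 | 6% |

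Combining every unfavourable assumption (two days, ρ = 0.5, τ = 2) gives (1 + 0.75 + 2)/4 = 0.9375, about 3% narrower.

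**Shared baseline error.** With τ = 0 and ρ = 0, changes at two visits share the baseline variance. Their errors correlate 1/2 = 0.50 with a single baseline and (1/3)/(4/3) = 0.25 with a three-day mean.

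**Illustration in ratio terms.** Assume a within-patient CV of 50%, so s = √ln(1.25) = 0.472 on the log scale, and ρ = 0. The multiplicative interval factor is exp(t × s × √(variance/n)). From the last-sample baseline to the three-day mean it falls:
- n = 15: from 1.45 to 1.35 (τ = 0), or from 1.57 to 1.49 (τ = 1);
- n = 10: from 1.61 to 1.48 (τ = 0), or from 1.80 to 1.68 (τ = 1).

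The CV is purely illustrative. The percentages in the table do not depend on it.

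**The case against.** **The rule is legitimate.** The last pre-dose value is clear, pre-specified and common to nearly all variables. Nothing contradicts it, and saliva has no test or precision target. This stands: the point is an inexpensive improvement, not the repair of an error.

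**The best case is unlikely.** A reader might infer an 18% gain, equivalent to 50% more patients (1/0.667 = 1.5). That needs identical true changes in all patients and independent errors. Doses are titrated individually, and baseline UFC in the early patients ranged from 1.6 to 17.0 × ULN, so identical changes are implausible. A reader might also infer that two thirds of the baseline saliva data are always lost, but a short baseline may hold only two days. Both limits stand.

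**Follow-up is equally noisy.** Later values remain single samples, so averaging the baseline removes at most one third of the modelled variance. UFC is averaged at both ends, which makes the analogy partial. This also stands.

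**Averaging could introduce drift.** Washout for steroidogenesis inhibitors is one week. If cortisol were still moving, the last value would be nearest the untreated state. Most of this is answered, because washout must finish before baseline efficacy assessments. Completing a minimum washout does not prove stability, however, so a last-value comparison is worth showing.

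**The change is late.** Earlier results of this open-label study are already in CSRs, so redefining baseline now is made with knowledge of data. That calls for disclosure and for both versions to be shown. Saliva would also have a different baseline rule from plasma ACTH and serum cortisol in the same analysis.

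**Conclusion.** The point holds as a modest, avoidable loss of precision in the salivary cortisol and aldosterone changes. Averaging the scheduled baseline days would narrow the 95% interval by roughly 4% to 18%, or about 3% if every unfavourable assumption applies together. The range rests on assumed values of τ and ρ, on two or three baseline days, on equal sample variances and on a stable baseline mean. Averaging gained precision in every scenario calculated.

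A reader might go further and infer that the salivary results are biased or that the efficacy conclusions are at risk. The documents do not support this. A single stable pre-dose sample gives a noisier baseline, not a shifted one; the salivary analysis is descriptive; and UFC response uses its own averaged values under SAP 8.4.

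**What to change.** Add to SAP 8.2, before the final database lock:

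*For salivary cortisol and salivary aldosterone, baseline is the mean of all valid scheduled pre-dose samples in the baseline period (Visit 2, within 20 days before Day 1 and after any required washout), calculated separately for morning and late-night samples. The geometric mean is used if change is analysed as a ratio. At least one sample is required, and the number of baseline days used is reported.*

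Defining the set by period and window, rather than by exact days, keeps patients with a shorter baseline or shifted collection days. Setting baseline by clock time also resolves the same-day ambiguity.

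Show the last-value baseline, again by clock time, as a sensitivity analysis. It gives continuity with earlier CSRs and a check for drift across the baseline period. State that the definition was changed after earlier results had been reported.

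The cost is a short SAP addition, a small change to the baseline derivation and one extra table; no new samples, visits or patients. The downsides are that salivary changes may differ slightly from earlier CSRs, and that saliva will follow a different baseline rule from the plasma hormones.

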### 8.3 Visit number

The time point (Day/Week) associated with an assessment, will be determined by the visit number assigned to the corresponding assessment in the database. The mappings of visit numbers to time points in the core study and the extension study are provided in the table below. Saliva samples as well as other ECG, lab and PK parameters collected not following protocol schedule may only be presented in listings and not included in any statistical analysis.

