Stage	A major subdivision of the study timeline; begins and ends with major study milestones such as enrollment, randomization, completion of treatment, etc.
Stop study participation	Point/time at which the patient came in for a final evaluation visit or when study drug was discontinued whichever is later.
Study drug	Any drug administered to the patient as part of the required study procedures; includes investigational drug and any control drugs.
Study drug discontinuation	Point/time when patient permanently stops taking study drug for any reason;
Subject	An individual who has consented to participate in this study. The term Subject may be used to describe either a healthy volunteer or a patient.
Variable	Information used in the data analysis; derived directly or indirectly from data collected using specified assessments at specified timepoints.
Withdrawal of Consent	Withdrawal of consent occurs only when a patient does not want to participate in the study any longer, and does not want any further visits or assessments, and does not want any further study related contact

Amendment 9 (03-May-2018)

Amendment Rationale

Of the 19 patients initially enrolled under Amendment 4, 10 patients are still ongoing as of 03 May 2018.

The purpose of this amendment is to extend the study end date from 31 December 2018 to 31 December 2019 to allow continued access to the study drug for those patients benefitting from the treatment until a separate long-term safety follow-up study (roll-over study) is set up at participating sites.

Additional updates were made to the Protocol glossary and withdrawal of informed consent section to align with the new Personal Data and Withdrawal of Consent language requirement.

Due to the extension of the study duration, this amendment is classified as substantial.

Changes to the protocol and the ICF

[figure not shown]
- Protocol synopsis and Sections 3.1, 5.5.15, and 6: Long Term Extension-2 end day changed from 31 December 2018 to 31 December 2019
- Glossary: Updated Personal Data and Withdrawal of Consent language
- Section 5.5.12 Updated Withdrawal of Consent language
- Updates to the ICF include updating the study end date from 31 December 2018 to 31 December 2019 throughout the document and the implementation of General Data Protection Regulation (“GDPR”) language for sites in the European Union.

IRB/IEC

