At Day 154, patients have the option to enter the 12 month extension phase at the investigators discretion provided they do not meet any discontinuation criteria. Dosing titration during the extension is to be based on efficacy (UFC control) and safety ([Section 5.5.4](#)). Patients will come in for monthly visits for the first 6 months (Day 154- Day 322) of the long-term extension and then will have visits every 3 months from month 6 through 12 (Day 322 - Day 490). At the end of the extension phase, patients will complete an End of Treatment-Extension visit at Day 490 and an End of Study visit 28 days after the last dose administration, if not continuing into long term Extension-2.

Optional long term extension-2

At Day 490, patients have the option to enter a second long term extension phase (extension-2) at the investigator's discretion, provided they do not meet any of the study discontinuation criteria. Dose adjustment during the extension is to be based on efficacy (UFC control) and safety ([Section 5.5.4](#)). Patients will come in for visits every 3 months during the first 18 months of extension-2 (approximately 3 years into the study), and every 6 months thereafter. This additional long term extension (extension-2) will provide important long term safety and efficacy data of LCI699 in patients with Cushing's disease.

1. Patient treatment in Long Term Extension-2 will end at each site within 4 months after a separate roll-over study is opened at their site, or by 31 December 2019 (whichever occurs

earlier). The roll-over study will provide an opportunity of continued treatment for patients who are still ongoing at that time and who are clinically benefitting from LCI699. For sites where a separate roll-over study is not an option, the patient may be offered a local alternative treatment option.

Patients entering the roll-over protocol will complete an EOT visit. For these patients the EOS visit is not applicable, as treatment on LCI699 will not be interrupted. Sites with the separate roll-over study option available, should arrange their patient's End of Treatment (EOT) visit within 4 months of the roll-over study being opened at their site (i.e. earlier than the 6 month visit intervals in Long-Term Extension-2), to allow their patients to continue their LCI699 dose on this new study.

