#### **7.5.2 Laboratory abnormalities**

For analyzing laboratory results, data from all sources (central and local laboratories) will be combined. The summaries will include all laboratory assessments up to data cut-off date. All laboratory assessments will be listed. Results will be reported for each visit at which collected in the core, follow-up, and extension phases through the last study visit.

Biochemistry, hematology, and urine laboratory data, will be presented using

- shift tables using CTC grades (if available), otherwise by normal ranges: both standards from baseline to most extreme post-baseline value and baseline to last value
- listings flagging values with elevated CTC grades (i.e. greater than 0), and outside of the normal ranges otherwise

All laboratory values will be converted into SI units and the severity grade derived using NCI Common Terminology Criteria for Adverse Events (CTCAE) v4.0. Blood glucose will be presented as mg/dL and will be assessed using the ADA criteria 2010. Insulin and QUICKI may also be presented in US unit. In the unlikely case a local laboratory normal range overlaps into the higher (i.e. non-zero) CTC grade, if the laboratory value is within local normal limits it will be assigned a CTC grade of zero.

The following summaries will be produced for the laboratory data (by laboratory parameter):

- Number and percentage of patients with worst post-baseline CTC grade (regardless of the baseline status). Each patient will be counted only for the worst grade observed post-baseline
- Number and percentage of patients meeting categorical liver function test criteria, including Hy’s Law criteria for liver injury (ALT or AST > 3 x ULN and TBIL  $\geq$  2 x ULN and ALP < 2 x ULN). Each patient will be counted only for the worst grade observed post-baseline
- Shift tables using CTC grades to compare baseline to the worst post-baseline values will be produced for hematology and biochemistry laboratory parameters with CTC grades
- For laboratory parameters in which CTC grades are not defined, shift tables to the worst post-baseline values will be produced using the low/normal/high classifications based on laboratory reference ranges
- Selected laboratory data will be also be displayed by presenting summary statistics of change from baseline values.

The following listings will be produced for the laboratory data:

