**Table 8-2 Visit number in extension phase**

Extension study Visit	Day/Week	Clarifying Notes
Visit 12	Day 154/Week 22	Long term extension 1
Visit 13	Day 182/Week 26	Long term extension 1
Visit 14	Day 210/Week 30	Long term extension 1
Visit 15	Day 238/Week 34	Long term extension 1
Visit 16	Day 266/Week 38	Long term extension 1
Visit 17	Day 294/Week 42	Long term extension 1
Visit 18	Day 322/Week 46	Long term extension 1
Visit 19	Day 406/Week 58	Long term extension 1
Visit 776	Day 490/Week 70/ End of Treatment Ext 1	End of treatment in extension phase 1
Visit 20	Month 16	Long term extension 2
Visit 21	Month 19	Long term extension 2

Extension study Visit	Day/Week	Clarifying Notes
Visit 22	Month 22	Long term extension 2
Visit 23	Month 25	Long term extension 2
Visit 24	Month 28	Long term extension 2
Visit 25	Month 31	Long term extension 2
Visit 26	Month 34	Long term extension 2
Visit 27	Month 40	Long term extension 2
Visit ...	Month ...	Long term extension 2
Visit 777	End of Treatment Ext 2	End of treatment in extension phase 2
Visit 778	28 days after last dose	End of study

After Visit 27 / Month 40, visits occur every 6 months. The Visit Number increases by 1 each time, and the Month increases by 6.

Unlike the above visits that are scheduled to occur after a fixed number of days have elapsed since Day 1, the Visits 777 (End-of-Treatment in core phase and extension phase) and 778 (End of study) are scheduled when the patient either completes the respective study phase or decides (or is mandated by the protocol) to prematurely discontinue from the study.

If such a visit happens neither too soon nor too late after the actual last scheduled visit, then it will be mapped to the next scheduled visit that would have occurred had the patient continued in the study. Otherwise, the early discontinuation visit will be mapped to an unscheduled visit.

The 777visit will be considered to have occurred neither too soon nor too late after the actual last scheduled visit if number of days between the two visits is

- i. at least half of the planned gap between the patient's actual last scheduled visit and the next scheduled visit and
- ii. at most the total of
  - a. the planned gap between the patient's actual last scheduled visit and the next scheduled visit (that would have occurred if the patient had not discontinued)
  - b. half of the planned gap between the patient's next two scheduled visits (that would have occurred if the patient had not discontinued).

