If the number of days between the 777visit and last scheduled visit (last scheduled visit +1) is less than the range specified above, then the 777visit will be mapped to an unscheduled visit of the last scheduled visit (last scheduled visit +1); if it's more than the range, then it will be mapped to an unscheduled visit of the last scheduled visit + 1 (last scheduled visit+2).

For example, if a patient's last scheduled visit is Visit 6, then his next two planned visits would have been Visit 7 and Visit 8 if he had not discontinued. Thus, the early discontinuation visit will be mapped to Visit 7 only if it occurs between 7 (Day 42 – Day 28)/2 and 21 (14 + (Day 56 – Day 42)/2) days after Visit 6.

Further, if a patient continued into the extension phase, then we set Visit 777 in the core phase to Visit 12 without checking the days-in-between. Visit 778 will not be mapped.

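### SAP 8.3 bars off-schedule laboratory values from any statistical analysis, SAP 7.5.2 counts them all, and the worst-grade, shift and Hy's Law tables depend on which rule is followed

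*SAP*

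**What the plan says.** SAP 7.5.2 (Laboratory abnormalities) pools central and local results and sets the scope of the tables: "The summaries will include all laboratory assessments up to data cut-off date". It then specifies the worst post-baseline CTC grade, a liver table that includes the Hy's Law criteria, and shift tables "from baseline to most extreme post-baseline value and baseline to last value". None of these entries mentions unscheduled samples.

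SAP 8.3 (Visit number) ties each assessment to a time point through its visit number. It then adds, for saliva samples and also for ECG, laboratory and PK data, that "lab and PK parameters collected not following protocol schedule may only be presented in listings and not included in any statistical analysis".

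Neither section refers to the other, and the SAP gives no order of precedence.

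The protocol generates laboratory samples outside the visit grid:
- Table 5-1 (section 5.5.5) asks for repeat liver tests, preferably within 48 to 72 hours of an abnormal transaminase result, followed by weekly monitoring.
- Section 5.5.6 asks for repeat testing of potential liver-injury cases.
- Section 6.6.4 makes repeats mandatory after a clinically relevant deviation, until it resolves or stops being relevant.

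**The concern.** Repeat and unscheduled samples are not a random subset. They are drawn because a value is already abnormal or a patient is unwell, so they are more likely than a routine panel to hold the peak. A table of worst values that omits them is biased towards safety.

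Read as a restriction, the 8.3 sentence contradicts 7.5.2. Read as a permission, it leaves open, in an open-label study, whether such values count, and that choice could be made after they have been seen. SAP section 3 says the Final CSR concentrates on long-term safety and efficacy, and the extensions are where scheduled panels are furthest apart.

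**Working it through.** The plan gives no figure for this point. The check compares the text, then considers direction and scale.

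**1. The two rules applied to the same sample.** Take a scheduled panel with ALT above 3 × ULN and bilirubin below 2 × ULN. A repeat within 72 hours shows ALT still above 3 × ULN, bilirubin at or above 2 × ULN and ALP below 2 × ULN. SAP 7.5.2 defines Hy's Law by those three limits.

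| Table in SAP 7.5.2 | Under 7.5.2 | Under 8.3 read literally |
|---|---|---|
| Worst post-baseline grade | repeat counts | scheduled value only |
| Shift to most extreme value | repeat counts | scheduled value only |
| Shift to last value | repeat counts if it is the last value | last scheduled value |
| Liver / Hy's Law | patient counted | patient not counted |
| Listings | shown | shown |

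**2. Direction.** For each patient, let S be the set of scheduled post-baseline grades and U the set of off-schedule grades. Then max(S) ≤ max(S ∪ U). The number of patients at or above any given grade can therefore only stay the same or fall when U is dropped. The same holds for Hy's Law if the criteria are judged on values from the same occasion, because removing occasions cannot create a case. The shift to last value has no fixed direction.

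**3. When it matters.** A patient is affected only if max(U) > max(S). If a scheduled panel already reached the same grade, nothing changes. The room for this grows with the gap between scheduled panels (Assessment schedules; month length 365.25/12 = 30.4375 days, following SAP 8.6):
- Day 322 to 406: (406 − 322)/7 = 12 weeks
- Day 406 to 490: (490 − 406)/7 = 12 weeks
- Extension-2, first 18 months: 3 × 30.4375/7 = 13.0 weeks
- Extension-2, thereafter: 6 × 30.4375/7 = 26.1 weeks

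Earlier panels are 2 to 4 weeks apart, and the tables pool all post-baseline time, so those dense early panels limit the effect.

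**4. Scale of one patient.** The documents do not say how many patients would have their worst grade off schedule. The Amendment 9 rationale reads: "Of the 19 patients initially enrolled under Amendment 4, 10 patients are still ongoing as of 03 May 2018". Taking 19 as the size of the All Patients column (an assumption), the exact (Clopper-Pearson) intervals are:
- 0/19: upper limit 1 − 0.025^(1/19) = 17.6%
- 1/19 = 5.3%: lower limit 1 − 0.975^(1/19) = 0.1%; upper limit 26.0%, which solves (1 − p)^19 + 19p(1 − p)^18 = 0.025

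As a check on the method, 1 − 0.025^(1/6) = 45.9%, which matches the SAP Table 10-1 entry for 0 of 6.

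Table 5-1 came in with Amendment 7, when 12 patients were ongoing (as of 30 November 2015), so at most about 12 of the 19 could be affected by that route. Section 6.6.4 is not among the sections that amendment lists as changed.

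**The case against.** The best defence is that ordinary reading resolves the conflict. SAP 7.5.2 is the section that specifies these tables, and it says the summaries will include everything. The 8.3 sentence sits under a heading about visit numbers and was probably meant for values with no slot in a by-visit table. That is likely the intent, and a careful programmer might follow it. But it is not written down, and 8.3 speaks of any statistical analysis.

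A second defence is that repeats required by the protocol do follow the protocol, so 8.3 does not reach them. This is arguable. The repeats are not in the Assessment schedules, and the SAP does not define the phrase, so the doubt remains.

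A third defence is that serious cases surface elsewhere. This stands. Section 5.5.6 makes a confirmed potential liver-injury case with no other cause an SAE. Section 6.6.4 sends clinically relevant deviations to adverse event evaluation. Both feed the AE summaries in SAP 7.5.1.3, and SAP 7.5.2 lists newly occurring grade 3 or 4 values. It lowers the stakes but does not correct the laboratory tables.

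Two stronger readings are tempting.
- **End-of-treatment panels.** A reader might infer that many of these would be lost. SAP 8.3 says of an ill-timed Visit 777, "Otherwise, the early discontinuation visit will be mapped to an unscheduled visit", and protocol 3.1 tells roll-over sites to hold this "visit within 4 months of the roll-over study being opened at their site (i.e. earlier than the 6 month visit intervals in Long-Term Extension-2"). For roll-over patients it is also the last panel: "For these patients the EOS visit is not applicable, as treatment on LCI699 will not be interrupted". The documents do not support the inference. The exclusion turns on how a sample was collected, not on its mapping label. The Assessment schedules list laboratory tests at that visit, and SAP 8.3 itself describes Visit 777 as scheduled. Its timing depends on when each site opens the roll-over study, which is not given, so no count can be supported.
- **Local laboratories.** A reader might cite protocol 6.5 as a further source of lost safety values. That sentence concerns UFC, hormones and related analytes. Hematology and chemistry are run locally as routine under 6.6.4.

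**Conclusion.** The contradiction is in the current text and should be removed. Applied literally, 8.3 would drop repeat and unscheduled safety samples from the worst-grade, shift and liver/Hy's Law tables, and it could only lower the worst-grade and Hy's Law counts.

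The size cannot be estimated from the documents. It is limited to patients whose worst grade never appears at a scheduled visit, and each such patient is worth about 5 percentage points if the denominator is 19. The conclusion assumes that protocol-required repeats count as off schedule, which the SAP leaves unclear.

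It would go too far to say that a true Hy's Law case would be hidden, because SAE reporting and the listings would show it. No primary result or decision rule depends on these tables. Severity is minor.

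**What to change.** Amend two places in the SAP.
- **Section 8.3:** state that off-schedule laboratory values are left out only of by-visit summaries and by-visit change from baseline.
- **Section 7.5.2:** state that worst post-baseline grade, shift to most extreme value, shift to last value, and the liver and Hy's Law tables use every post-baseline value up to data cut-off, scheduled or unscheduled, central or local. For clarity, add that this includes any Visit 777 panel mapped to an unscheduled visit.

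The cost is two sentences, to be settled before database lock, plus a check that the table programs follow them. No protocol amendment, visit or sample is needed, because the values are already collected and listed.
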